9.1.5 Secondary Efficacy Analysis

A two-sided 0.05 alpha level will be used.

For comparison of biomechanical measurements between a preoperative plan and postoperative measurements within the Rejuvenate[®] Modular Hip System group, a t-test or Wilcoxon test will be used.

Independent group t-tests will compare HHS, SF-12 and LEAS at each time point between the Rejuvenate[®] Modular Hip System and Secur-Fit[™] HA monolithic femoral stem groups. In addition, a paired t-test will compare the results preoperatively with each postoperative evaluation within the Rejuvenate[®] Modular Hip System group.

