9.2.2 Safety Analysis

All AEs will be listed, tabulated and summarized by event, number and percent of cases/subjects. AE rates and 95% confidence intervals will be presented. In addition, a

CONFIDENTIAL

Fisher's exact test will be used to compare the AE rates between the Rejuvenate® Modular Hip System and the Secur-Fit™ HA groups or cohorts, if appropriate.

For categorical variables, such as radiographic stability, the number and percent in each category will be presented.

9.3 *Missing Data*

No missing data will be imputed for the primary analysis and secondary analyses.

9.4 *Statistical Methodology*

9.4.1 *Data Summary*

The following is a detailed proposal of statistical analyses planned for data collected during the study.

Descriptive statistics will be computed for all preoperative conditions and demographic parameters. That is, for continuous data (e.g. HHS) the N, mean, median, standard deviation, minimum and maximum will be computed. For categorical data (e.g. gender) the frequency will be computed. If appropriate, the data will be presented by the Rejuvenate® Modular Hip System and the Secur-Fit™ HA groups.

Descriptive statistics and statistical comparisons for important demographic, efficacy and safety variables will be provided in tables.

A survival analysis for revision/removal of the modular femoral stem/neck construct will be performed.

9.4.2 *Sample Size Calculation*

Given an estimated revision rate for both groups at 2.5% and a non-inferiority margin of 5%, with a one-sided alpha of 0.05 and 80% power, a total of 147 cases per group are required to reject the null hypothesis that the revision rate for Rejuvenate® Modular Hip System cases is 5% greater than for Secur-Fit™ HA monolithic femoral stem cases. In order to control for a 20% drop-out rate, 183 cases per group are required.

CONFIDENTIAL

A total of 240 cases received the Secur-Fit™ HA femoral stem in the Trident® X3® Polyethylene Insert Study, a historical control. Therefore, although only 183 cases are needed for statistical power, 240 cases will be enrolled in the Rejuvenate® Modular Hip System Outcomes Study.

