9.4.4 Patient Populations

Modified Intent-to-Treat (ITT) Population: The study population for analysis will include all subjects who receive the Rejuvenate® Modular Hip System or the Secur-Fit™ HA monolithic femoral stem. This does not include cases censored from analysis for a reason that may have a significant impact on outcome.

The primary and secondary efficacy analyses will be based on the per protocol population.

Per Protocol Population: The study population will include all subjects who receive the Rejuvenate® Modular Hip System or the Secur-Fit™ HA monolithic femoral stem. This does not include cases that have major protocol violations including the violation of entry criteria. In order for cases to be included in the per protocol population, the data required for analysis of a specific parameter must be present. Any data of secondary variables will be included, where possible.

The primary efficacy analyses and safety analysis will be based on the modified ITT population; the secondary efficacy analyses will be based on the per protocol population.

10 Study Procedures

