10.3 Early Withdrawal of Subjects

When and How to Withdraw Subjects

In the event that the subject is discontinued by the investigative center prior to the final study evaluation, the subject will be notified by the center that he/she is no longer in the study and a Study Termination CRF will be completed.

The following is a list of reasons for which subjects may be withdrawn and the date of termination that should be used on the Study Termination CRF in each situation. This list is not all inclusive:

Termination Reason	Date of Termination
Death	Date of death
Investigative center termination	Date of study close-out visit
Lost to follow-up	Date Stryker termination approval given
Voluntary withdrawal	Date subject notified center of withdrawal
Revision/removal of study device	Date of revision/removal procedure
Study device not implanted	Date of surgery
Surgery not performed	Date Stryker termination approval given

At the time of study surgery it is required that the following components are implanted:

- Rejuvenate® Modular Stem
- Rejuvenate® Modular Neck
- Stryker Trident® or Tritanium™ Primary acetabular shells, with or without screw fixation, as well as Stryker Restoration® ADM acetabular shells
- Stryker alumina ceramic inserts (for use with Trident® acetabular shells) or X3® inserts
- Stryker LFIT™ CoCr heads; delta ceramic heads; or alumina ceramic heads with adapter sleeve

Revision or removal of the Rejuvenate® Modular stem/neck construct constitutes a failure and study termination for the subject.

CONFIDENTIAL

If acetabular insert or femoral head exchange is required during the study, the event is considered a reoperation and does not constitute a failure or study termination.

If acetabular shell and insert revision is required during the study, the event is considered a reoperation and does not constitute a failure or study termination.

If the subject fails to return for his/her follow-up appointments, every effort should be made to contact the subject to assess his/her health status. If after attempting to contact the subject through three documented phone calls and a certified letter, the subject still does not respond, he/she will be considered lost to follow-up. A Study Termination CRF will be completed only after notifying Stryker of the subject's status and being given approval to terminate.

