INVESTIGATOR NAME (PRINT): _____

INITIAL/DATE:

INVESTIGATOR SIGNATURE: _____

Stamp Date Received: _____

Receipt _____

DATE: / /
 D D M M M Y Y Y Y

For Stryker Use Only

Entry _____

Verification _____

Monitored _____

[name]

SUBJECT ID: **6 8**
 Study # Site # Subject #**GENERAL INFORMATION**SUBJECT INITIALS:
(If there is no middle initial please use "-") ONSET DATE: / /
 D D M M M Y Y Y Y**III. TREATMENT** Yes* No

* If Yes, specify below

REVISIONS / REMOVALS: (Check all that apply)

- Acetabular Shell
- Acetabular Insert
- Femoral Bearing Head
- Modular Neck / Modular Stem (Complete Study Termination form)
- Other

For Stryker Implants, submit PER form and implant(s) to Stryker.

Date of Treatment

 /  / 
 /  / 
 /  / 
 /  / 
 /  / 
D D M M M Y Y Y Y

RE-OPERATIONS: (Specify)

-
-

 /  / 
 /  / 
D D M M M Y Y Y Y

OTHER TREATMENTS: (Specify)**ANESTHESIA USED?** Yes No

-
-
-
-
-

 /  / 
 /  / 
 /  / 
 /  / 
 /  / 
D D M M M Y Y Y Y

RESOLUTION OF EVENT:

- Unresolved as of
- Resolved as of

* Submit copy of this form when event resolved.

 /  / 
 /  / 
D D M M M Y Y Y Y

*

IV. COMMENTS**INVESTIGATOR NAME (PRINT):** **For Stryker Use Only**

INITIAL/DATE:

Receipt _____

INVESTIGATOR SIGNATURE:

Stamp Date Received:

Entry _____

DATE: / /
 D D M M M Y Y Y Y

PER#.

Verification _____

Monitored _____

SUBJECT ID:

6 8

Study #

Site #

Subject #

GENERAL INFORMATION

SUBJECT INITIALS:

--	--	--

(If there is no middle initial please use " - ")

OPERATIVE SIDE: (use one form per side)

 Right Left

DATE OF

DEVIATION:

--	--

D D

--	--	--

M M M

--	--	--

Y Y Y

--	--	--

Y Y Y

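### From the date of stem/neck revision, Rejuvenate hips drop out of the HHS, SF-12 and LEAS comparisons, so the planned t-tests describe only hips that kept their construct, and the plan does not say so

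*Combined protocol and SAP*

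**What the plan says.** **The comparison.** Section 9.1.5 reads "Independent group t-tests will compare HHS, SF-12 and LEAS at each time point between" the two device groups. It adds paired t-tests of each postoperative evaluation against the preoperative value within the Rejuvenate group. On the error rate it says "A two-sided 0.05 alpha level will be used". Section 2.1.2 presents the scores as a comparison of pain, function and quality of life between the groups and expects the study group to be non-inferior. No score margin is given.

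**What happens at revision.** Section 10.3: "Revision or removal of the Rejuvenate® Modular stem/neck construct constitutes a failure and study termination for the subject". The termination date is the date of the procedure. The adverse event form in Appendix F agrees, with the entry "Modular Neck / Modular Stem (Complete Study Termination form".

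**What does not end participation.** For head or insert exchange, and for shell and insert revision, section 10.3 says "the event is considered a reoperation and does not constitute a failure or study termination".

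**Missing scores.** Section 9.3: "No missing data will be imputed for the primary analysis and secondary analyses".

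**Analysis set.** Section 9.4.4 assigns the secondary efficacy analyses to the per-protocol population, for which "the data required for analysis of a specific parameter must be present".

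Nothing in the documents collects these scores after a stem/neck revision, assigns a value to a failed hip, or plans a sensitivity analysis for it.

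**The concern.** Each rule is unremarkable alone. Together they remove a Rejuvenate hip from every score comparison after its stem/neck construct is revised. The reason for the missing score is the primary endpoint itself, so the missingness is tied to the outcome on which the devices are being compared.

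The stated objective is a comparison of devices. The planned test answers a narrower question: how do hips score while the construct is still in place? If Rejuvenate had more stem/neck revisions and revised hips would have scored lower, its later means would rise relative to a comparison of all implanted hips. The secondary results could then look better as the primary result got worse. With no score margin, a non-significant two-sided test could be read as meeting the expectation of non-inferiority, and nothing in the table would show how many hips had left because the device failed.

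**Working it through.** The documents give no sample size, effect, SD or margin for the scores, so there is no plan figure to reproduce. The check has two parts: whether the rules combine as described, and how large the effect could be.

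**1. The rules, for a Rejuvenate hip with stem/neck revision between two visits**
- Visits before revision: scores were collected and are kept.
- Visits after revision: the subject has been terminated (10.3), so there is no score.
- No value is imputed (9.3), and without the score the hip is not in the analysis set for that parameter (9.4.4).
- It is therefore absent from the between-group and paired t-tests at each later visit.
- A hip with only a head, insert or shell procedure stays in.

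**2. Formula.** Let r be the cumulative proportion with stem/neck revision, and let the gap be the mean score of unrevised hips minus the mean that revised hips would have had.
- All-hips mean = unrevised mean − r × gap, so omitting revised hips raises a group's mean by r × gap.
- If both groups drop revised hips: net bias = (r_T − r_C) × gap, taking the same gap in each.
- If only Rejuvenate drops them: net bias = r_T × gap.

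**3. Inputs**
- r_C = 2.5%, the planning rate for both groups (9.4.2).
- r_T = 2.5% (plan), 5% (illustrative) and 7.5% (2.5% plus the 5% margin in 9.1.4 and 9.4.2).
- Gap: assumed 20 to 40 HHS points. SD: assumed 12 to 15. Neither is in the documents.
- Hips per group: 240 × (1 − 0.20) = 192, from the enrolment figure and drop-out rate in 9.4.2.

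**4. Results, HHS at year 5, in points towards Rejuvenate**

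| r_T against 2.5% | Rejuvenate revisions in 240 | Net bias if both groups drop revised hips | Net bias if only Rejuvenate does |
|---|---|---|---|
| 2.5% | 6 | 0 | 0.5 to 1.0 |
| 5% | 12 | 0.025 × 20 = 0.5 to 0.025 × 40 = 1.0 | 1.0 to 2.0 |
| 7.5% | 18 | 0.05 × 20 = 1.0 to 0.05 × 40 = 2.0 | 1.5 to 3.0 |

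Section 9.1.3 gives a 7% margin instead. At 9.5% against 2.5% the net bias with both groups dropping would be 0.07 × 20 = 1.4 to 0.07 × 40 = 2.8.

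**5. Scale**
- SE of the difference = SD × √(2/192): 1.22 at SD 12 and 1.53 at SD 15.
- The 0.5 to 2.0 point range is therefore 0.5/1.53 = 0.33 SE to 2.0/1.22 = 1.63 SE.
- Suppose the true all-hips deficit for Rejuvenate were just detectable with 80% power at two-sided 0.05, which is 1.96 + 0.84 = 2.80 SE. A bias of 0.33 SE leaves power Φ(2.80 − 0.33 − 1.96), about 70%. A bias of 1.63 SE leaves Φ(2.80 − 1.63 − 1.96), about 21%.

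These are cumulative 5-year rates. Fewer hips will have been revised at earlier visits, so the effect there is smaller. SF-12 and LEAS are not sized.

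**The case against.** The best defence is that comparing scores while the construct is in place is a recognised choice when failure has its own endpoint. Failure is well covered here: it is the primary endpoint, it appears in the Kaplan-Meier curve, and revision rates are a safety parameter (9.1.4, 9.2.1, 9.4.1). Scores before revision are kept, so a painful failing hip counts until it is revised. Section 9.4.4 also includes secondary data where possible.

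Much of this stands. The remaining weakness is that the plan neither names that choice nor labels the score comparison accordingly, and reporting failures elsewhere does neither. Including data where possible cannot help when no score is collected after termination.

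A reader might infer four stronger things that the documents do not support:
- *Every revised hip is excluded, so the bias favours whichever device fails more.* The termination rule is written for the Rejuvenate construct only. The documents do not say whether revision ended follow-up in the historical control study. Acetabular and head procedures stay in for Rejuvenate.
- *A worse primary result could be concealed.* It could not, because revisions are counted and reported in their own right.
- *A formal non-inferiority conclusion on scores is inflated.* Without a score margin, no such conclusion is defined. Section 2.1.2 states only an expectation.
- *The hips lost are known to be the worst scorers.* This is a reasonable inference, but no data in the documents show it.

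**Conclusion.** The concern holds in a limited form. For Rejuvenate, the between-group and paired t-tests at visits after a stem/neck revision describe only hips without one, and the plan presents them as a comparison of devices without saying so. This follows from the text and needs no assumption.

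The size does rest on assumptions: the score deficit and SD are not in the documents, and the direction depends on Rejuvenate having the higher revision rate or on control hips having stayed in after revision. If the control study also dropped revised hips, the bias runs from zero at the planning rates with equal deficits up to 2.0 HHS points (1.63 SE) at year 5 with 7.5% against 2.5%. The upper end combines the largest excess, the largest deficit and the smallest SD. If the control study kept them, the bias towards Rejuvenate is larger and is not zero even at equal rates. The change is worth making because the effect is negligible only when the failure rates are similar, which is the question the study is meant to answer.

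**What to change.** In section 9.1.5:
1. Label the between-group and paired t-tests 'among hips without stem/neck revision'. A plain 'unrevised' would be wrong, because the adverse event form lists shell, insert and head procedures among revisions and those hips remain in follow-up.
2. Beside each visit's comparison, show the cumulative number of hips with stem/neck revision in each group.
3. Add a supplementary rank-sum comparison for each score at each visit, in which hips with stem/neck revision before that visit are ranked lowest in both groups.
4. Establish and state how the control study handled scores after revision, then apply the same rule to control hips.

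Cost: SAP wording and one extra analysis per score and visit. For Rejuvenate no new data are needed, since revision dates are already recorded on the Study Termination and adverse event forms. For the control group the primary analysis already needs revision status. The documents do not confirm that control scores can be linked to revision dates, so this must be checked.

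Downside: the ranked result mixes function with revision, which is most debatable for a general health measure such as SF-12. It should be supportive and should not replace the t-test. Missed visits in hips that keep their construct are a separate matter and are not addressed by this change.

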9.1.4 Primary Efficacy Analysis

A case success is defined as no incidence of femoral stem/neck construct revision/removal. The 90% confidence interval around the difference in success rate (Rejuvenate[®] Modular Hip System – Secur-Fit[™] HA monolithic femoral stem) will be computed at 5 years postoperative. For the non-inferiority comparison, the lower bound of this 90% confidence interval will be compared with -5%. If it is greater than -5%, non-inferiority is supported. In addition, if it is greater than 0%, superiority is supported. The Kaplan-Meier survival curve will also be displayed using SAS/PROC LIFETEST.

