*Data from the following Stryker sponsored clinical studies was used as a basis for this table: Omnifit® HA, ABC/Trident®, Meridian®, Citation®, Secur-Fit™, Accolade® TMZF and Trident® X3®. There were 2,966 total cases (hips) in 2,697 subjects after combining results from these seven studies. Percentages for operative and device related events were calculated by dividing the number of cases with one or more reported event by the number of cases (hips) enrolled. Systemic events were calculated by dividing the number of subjects with one or more reported events by the number of subjects enrolled. The protocols for the Omnifit® HA and ABC/Trident® studies originally required that all AEs be reported; however, after these products became commercially available, the protocols were modified and required that only operative related events be reported. For the ABC/Trident®, this change occurred in February 2003 and for the Omnifit® HA, in December 1990. The protocol for the Trident® X3® and Accolade® TMZF studies required that operative site AEs and any event meeting the definition of a serious event be reported. The protocols for Secur-Fit™, Citation® and Meridian® required that all AEs were reported. Percentages for primary THR taken from published literature represent averages or ranges as noted.

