Discharge Date:

--	--	--

 /

--	--	--

 /

--	--	--

D D / M M M / Y Y Y Y**III. COMMENTS**

--	--

INVESTIGATOR NAME (PRINT):

INVESTIGATOR SIGNATURE:

DATE:

--	--	--

 /

--	--	--

 /

--	--	--

D D / M M M / Y Y Y Y

Stamp Date Received:

For Stryker Use Only

INITIAL/DATE:

Receipt _____

Entry _____

Verification _____

Monitored _____

[name]

SUBJECT ID: **6 8** Study # Site # Subject #

GENERAL INFORMATION

SUBJECT INITIALS:
(If there is no middle initial
please use "-")

OPERATIVE SIDE: (use one form per side)

 Right LeftVISIT: Pre-Op 6 Week 1 Year 2 Year 3 Year 4 Year 5 Year 7 Year 10 Year

I. SF-12v2™ Health Survey Standard Version

This survey asks for your views about your health. This information will help keep track of how you feel and how well you are able to do your usual activities. *Thank you for completing this survey!*

For each of the following questions, please mark the circle that best describes your answer.

1) In general, would you say your health is: (Check one)

Excellent 	Very Good 	Good 	Fair 	Poor 
---------------------------------	---------------------------------	----------------------------	----------------------------	----------------------------

2) The following questions are about activities you might do during a typical day. Does your health now limit you in these activities? If so, how much?

	Yes, limited a lot 	Yes, limited a little 	No, not limited at all 
a. Moderate activities, such as moving a table, pushing a vacuum cleaner, bowling, or playing golf (Check one)			
b. Climbing several flights of stairs (Check one)			

3) During the past 4 weeks, how much of the time have you had any of the following problems with your work or other regular daily activities as a result of your physical health?

	All of the time 	Most of the time 	Some of the time 	A little of the time 	None of the time 
a. Accomplished less than you would like (Check one)					

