 - The subject may redeem 300 points (or any lesser amount of points in 100-point increments) for completing three postoperative visits according to protocol. If a subject chooses to redeem 300 points, he/she could either receive the Level C award booklet or Level A and Level B booklets at once.
 - As the subject continues in the study, the number of points already redeemed is deducted from the number of points that would have been available for redemption at each later visit. For instance, after 10 years if 300 points were already redeemed, the subject would only be eligible for 400 points upon study closure.
 - The maximum number of points that can be redeemed over the course of the study is 700.
- Bilateral subjects do not accumulate double points. Points are accrued per subject, not per hip enrolled.
- When subjects have completed the study by reaching the 10-year follow-up visit, they request an award booklet and order form from their SC. The award booklet will only contain the awards that the patient is eligible to receive according to the total gift level they have earned at that time. The subject selects the award and completes and mails in the order form. Awards may also be redeemed online at www.ecgy.net.
- All awards will be shipped directly to the subject's address (no P.O. boxes) with postage and/or shipping charges prepaid by Stryker. In the event a parcel arrives in a damaged or unsatisfactory condition, the SC is notified so that Stryker may be informed. Rewards should not be returned without specific instructions.
- Please allow 3 to 6 weeks for delivery. If, in the rare instance, the selection cannot be delivered immediately, the subject will be notified by postcard. If the selection becomes unavailable, it may be substituted with another selection from the same award level. Samples of prizes at each award level follow.

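### The hip-level tests have no rule for subjects with both hips enrolled, so applied to cases as written they understate standard errors, by a modest amount that matters most for SF-12 and LEAS

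*Combined protocol and SAP*

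**What the plan says.** **Unit.** Section 9.1.4 sets the primary endpoint by case: "A case success is defined as no incidence of femoral stem/neck construct revision/removal". The sample size (Section 9.4.2) and enrolment (Section 3.3) are also in cases. The footnote to Table 4 in Section 12.3 shows that a case is a hip: "There were 2,966 total cases (hips) in 2,697 subjects after combining results from these seven studies".

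**Two hips per subject.** The retention program in Appendix G provides for bilateral subjects: "Points are accrued per subject, not per hip enrolled". Appendix A asks for duplicate films for them. No criterion in Section 4 limits a subject to one hip.

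**Forms.** The SF-12 form in Appendix F reads "OPERATIVE SIDE: (use one form per side", and the LEAS form carries the same instruction. Section 2.1.2 describes the SF-12 as a measure of general health and the LEAS as a measure of the patient's activity level.

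**Tests.** Section 9.1.5 says "A two-sided 0.05 alpha level will be used". Between the groups, "Independent group t-tests will compare HHS, SF-12 and LEAS at each time point", and within the study group "a paired t-test will compare the results preoperatively with each postoperative evaluation". Section 9 contains no one-hip rule, person-level collapse, mixed model, GEE or cluster-robust variance.

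**The concern.** A two-sample t-test, a paired t-test and an ordinary interval for a difference in proportions all take records as independent. Two hips of one person share that person's age, health, activity and, often, surgeon. For hip-specific outcomes such as HHS and revision, some positive correlation is to be expected. For SF-12 and LEAS the problem is sharper, because a bilateral subject answers the same person-level questions on two forms. If both forms enter the test, one person's answers count almost twice.

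The sponsor already separates the two units elsewhere. The Table 4 footnote divides operative and device events by hips and systemic events by subjects. The efficacy tests have no matching rule.

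At stake is the nominal error rate of the secondary comparisons and, to a smaller degree, the coverage of the primary 90% interval.

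**Working it through.** **The plan's own figure.** Section 9.4.2 states 147 cases per group (2.5% revision in both groups, 5% margin, one-sided 0.05, 80% power), raised to 183 for 20% dropout. The simple unpooled formula gives 121 and the continuity-corrected one 158. Exact enumeration of the Farrington–Manning score test first reaches 80% power at 149 and gives 77.7% at 147, so the stated figure is approximately reproduced. The dropout step is 147/0.8 = 183.75. All of these calculations assume independent cases. The plan gives no figure for the secondary t-tests.

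**Bilateral share (assumption).** Neither this study's share nor the control group's is stated. The pooled figure from the sponsor's seven studies, which include the Trident X3 study that supplies the control, gives:
- extra hips: 2,966 − 2,697 = 269
- share of hips in pairs, if each extra hip is a second hip: f = 2 × 269/2,966 = 538/2,966 = 18.1%
- in 240 hips: 240 × 0.181/2 ≈ 22 bilateral subjects

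**Formulas.** For n hips with share f in pairs and within-person correlation ρ, the variance of the mean is multiplied by DE = 1 + fρ. The correct standard error is √DE times the naive one. The actual two-sided error of a nominal 5% test is 2[1 − Φ(1.96/√DE)]. The effective number of cases is 240/DE.

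**Results at f = 18.1% in both groups:**

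| ρ | DE | Correct/naive SE | Actual two-sided error | Simulated | 240 cases act like |
|---|---|---|---|---|---|
| 0.3 | 1.05 | 1.027 | 5.6% | 5.6% | 228 |
| 0.5 | 1.09 | 1.044 | 6.1% | 6.1% | 220 |
| 0.8 | 1.15 | 1.070 | 6.7% | 6.7% | 210 |
| 1.0 | 1.18 | 1.087 | 7.1% | 7.2% | 203 |

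The simulation used 240 hips per group, 22 bilateral subjects in each, and 200,000 runs. At ρ = 1 the correct error is 8.7% larger than the naive one, so the naive one is 1 − 1/1.087 = 8.0% too small.

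**Sensitivity.**
- Bilateral subjects in one group only, ρ = 1: DE for the difference = (1.181 + 1)/2 = 1.091, error 6.1%.
- Share 5–40%, ρ 0.3–1.0: error 5.2–9.8%.

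**Primary endpoint.**
- At assumed ρ of 0.1–0.5, DE = 1.018–1.091. The one-sided error is 1 − Φ(1.645/√DE) = 5.2–5.8%.
- After 20% dropout, 240 × 0.8 = 192 hips, which act like 192/1.091 = 176 to 192/1.018 = 189, above 147.
- Even at ρ = 1, the requirement is 147 × 1.181 = 174, or 218 after dropout, below 240.
- At a 30% share and ρ = 1 it is 239. It passes 240 only at a share of about 40% with ρ of 0.8 or more (243).

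**The case against.** The strongest reply is that double entry is inferred. Section 9.1.5 names no unit for the t-tests, and Section 9.4.4 defines the populations by subjects and then speaks of cases. A per-side form is a collection instruction, and the Demographics form, also person-level, carries it too. The Table 4 footnote shows that the sponsor can use a per-subject denominator where that fits. This stands as a limit: the documents do not show that both forms will be analysed. It does not remove the gap, because the primary analysis is explicitly by case and nothing in Section 9 supplies a different unit or a variance rule.

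Three stronger readings are tempting, and the documents support none of them.

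- *Every hip-level result is biased in favour of the device.* Section 2.1.2 expects non-inferior scores, but Section 9.1.5 plans two-sided difference tests. Their excess error produces false differences in either direction. No intervals are planned there for these scores.
- *The SF-12 and LEAS tests run at 7.1%.* That needs an 18% share in both groups and near-identical paired forms. With staged surgery the two hips reach each visit on different dates, so the correlation falls below 1.
- *The primary analysis is underpowered or invalid.* At the sponsor's share the effect is small and the planned 240 cases cover it.

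**Conclusion.** The concern holds as a gap in the plan with a modest, one-directional effect on precision: for any positive within-person correlation, the tests as written for cases understate the standard error. The 3–9% shortfall and the 5.6–7.1% error range rest on the sponsor's pooled hip-to-subject ratio holding in both groups, on each extra hip being a second hip, and on correlations of 0.3–1.0. None of these is given for this study.

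The main consequence is for SF-12 and LEAS. HHS and the pre/post changes are affected less if their within-person correlation is lower. The primary conclusion is touched only slightly. The change should be made before analysis, but the point does not call the sample size into question.

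**What to change.** In Sections 9.1.4 and 9.1.5:

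1. Name the subject as the cluster for every hip-level analysis.
2. Analyse SF-12 and LEAS with one record per person per visit, under a prespecified index-hip rule (for example, the first enrolled hip). Without such a rule, a visit is undefined for staged bilateral subjects.
3. Use subject-clustered robust standard errors or GEE for HHS, for hip-level pre/post changes and for the primary difference in success rates.
4. Report the number of bilateral subjects in each group.

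**Cost.** No new patients, visits or data are needed for the study group. At the sponsor's share, intervals widen by at most about 9% (ρ = 1), or by up to 14% if 30% of hips are bilateral (√1.30 = 1.14). For the primary interval at ρ of 0.1–0.5 the widening is about 1–4% (√1.018 to √1.091).

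**Linkage** must be checked. The study forms carry a subject ID and side, but the ID is assigned from a per-side form, and the documents do not say whether a bilateral subject keeps one ID. The historical control's data structure is not described, so linkage of hips to subjects has to be confirmed there as well.
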